8.1.3 Phone Contact 1 (1 week post treatment)

The study coordinator will call to review the temperature log and assess for any adverse events. The study coordinator will inform the PI immediately if any subject reports an oral temperature of >100.4. The PI or other trained physician will phone triage patients reporting elevated temperatures and bring them in for a study visit / direct them to the emergency room if necessary. If a subject is asked to come in for a visit, the visit will follow the procedures described in section 9.1.8.

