8.1.2.1 Post-PMT Administration monitoring: Bedside for 60 Minutes

Subjects will be monitored at 30 and 60 minutes following completion of PMT administration. Subjects will be visually observed for signs of aspiration or other respiratory distress, abdominal pain, vomiting, other signs of allergic reaction, and changes in vital signs. Vital signs (temperature, heart rate, respiratory rate, blood pressure, and oxygen saturation) will be checked. The following vital sign changes will be recorded if observed: (1) heart rate increase or decrease by greater than or equal to 30 beats per minute; (2) respiratory rate increase or decrease by greater than or equal to 10 breaths per minute or if respiratory rate drops below 10 or increases above 25 (if respiratory rate not already outside these ranges); (3) temperature: increase or decrease by greater than or equal to 2 degrees Fahrenheit, or if temperature drops below 96°F or increases above 100.4°F (if temperature not already outside these ranges); (4) oxygen saturation decrease by greater than or equal to 5% (sustained for more than 20 seconds) or if oxygen saturation drops below 90% (on current amount of oxygen delivered, sustained for more than 20 seconds); (5) blood pressure decrease by more than 30 mmHg systolic or 15 mmHg diastolic, or if blood pressure drops below 90/60 (if blood pressure not already outside these ranges).

During the monitoring period, information will be solicited from the patient regarding the following adverse events associated with FMT including aspiration, belching, bloating, nausea, vomiting, gastroesophogeal reflux, abdominal cramps, abdominal pain, diarrhea, and constipation.

Subjects will be sent home with:

- Second one-week BM diary. The diary will include a card for the collection of all solicited adverse events.
- Thermometer

- Temperature and Adverse Events log form
- Stool Collection Kit

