8.2 Safety and Other Assessments

For all women of childbearing potential, a urine pregnancy test will be performed prior to FMT and at all subsequent study visits. If a subject's urine pregnancy test is positive prior to treatment with FMT, the subject will be removed from the study. It is recommended that women not become pregnant as it is unknown how this treatment will effect pregnancies. If a subject does become pregnant on study, the pregnancy will be followed.

To monitor for signs of infection subjects will be required to keep a temperature log for 7 days following FMT (a digital thermometer will be provided). Subjects will be instructed to call the study doctor if their temperature rises above 100.4 degrees or drops below 96 degrees. The study doctor will phone triage patients reporting elevated temperatures and bring them in for a study visit or direct them to the emergency room if necessary.

Subjects will also be provided with a card for the collection of all solicited adverse events in their study diary. The card will be reviewed with the diary for any adverse events.

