8.3.3.3 Expectedness

We expect that gastrointestinal symptoms (including fever, aspiration, belching, bloating, nausea or vomiting, gastroesophageal reflux, abdominal cramps, abdominal pain, diarrhea, constipation) may be common post administration of the investigational products, both as a consequence of the underlying disease being treated, and potentially as an adverse effect of the administered product.

In the initial, 60-minute bedside observation period following administration of investigational product, subjects will be monitored with close attention to the following:

- allergic reaction (temperature, skin rash, heart rate, or blood pressure change as already described)
- sepsis or shock (temperature, heart rate, or blood pressure change as already described)
- bowel injury (abdominal pain change)
- aspiration (respiratory rate or oxygen saturation change)
- gastrointestinal symptoms (belching, bloating, nausea, vomiting, GERD, abdominal cramps, abdominal pain, diarrhea, and constipation)

In the subsequent, 7-day monitoring period following administration of investigational product, subjects will be monitored with close attention to the following:

- donor-derived infection (temperature or abdominal pain change)
- gastrointestinal symptoms (aspiration, belching, bloating, nausea, vomiting, GERD, abdominal cramps, abdominal pain, diarrhea, and constipation)

In the subsequent, 28-, 48-, and 180-day monitoring periods, subjects will be monitored with close attention to the following:

- transmitted infection (temperature or abdominal pain change as already described)
- metabolic changes (polydipsia, polyuria, weight gain, or weight loss)

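### Subjects are told to call for a home temperature above 100.4 or below 96, but the coordinator's notice to the PI and the physician's triage are written for high readings only

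*Combined protocol and SAP*

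**What the plan says.** Four places in the protocol deal with temperature after FMT.

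- **Section 8.2, purpose:** "To monitor for signs of infection subjects will be required to keep a temperature log for 7 days following FMT".
- **Section 8.2, subject's duty:** she is to phone the study doctor "if their temperature rises above 100.4 degrees or drops below 96 degrees". The next sentence gives the physician's response: "The study doctor will phone triage patients reporting elevated temperatures", followed by a study visit or referral to the emergency room if needed.
- **Section 8.1.3, one-week call:** the coordinator reviews the log and asks about adverse events. The notification rule is "The study coordinator will inform the PI immediately if any subject reports an oral temperature of >100.4". The physician step is "The PI or other trained physician will phone triage patients reporting elevated temperatures".
- **Section 8.1.2.1, bedside hour:** a temperature change is recorded "if temperature drops below 96°F or increases above 100.4°F", or if it moves by at least 2°F in either direction.
- **Section 8.3.3.3, what to watch for:** in the 7-day period, "donor-derived infection (temperature or abdominal pain change"); in the later periods, "transmitted infection (temperature or abdominal pain change as already described").

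**The concern.** The plan sets a lower limit for the subject and then does not carry it through to the staff. The mismatch is visible within 8.2 itself, where one sentence asks for a call at a low reading and the next provides triage only for high ones. No reason is given for dropping the lower limit at that point.

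The log is there to detect infection, and section 2.3.1 lists donor-derived infection among the most severe possible risks. Under section 8.3.8, a suspected donor-to-patient transmission pauses PMT administration across the study. That rule can work only if possible signs reach a physician. The one-week call is the scheduled check on readings that a subject did not phone in, and for a low reading it carries no instruction to escalate.

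**Working it through.** The protocol gives no figure to reproduce. The check is a comparison of limits and actions.

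| Step | Section | Above 100.4 | Below 96 |
|---|---|---|---|
| Bedside recording | 8.1.2.1 | yes | yes |
| Subject phones study doctor | 8.2 | yes | yes |
| Coordinator informs PI at log review | 8.1.3 | yes | not mentioned |
| Physician triage | 8.1.3, 8.2 | yes | not mentioned |

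The rows are not independent safeguards. Triage follows from either the subject's call or the coordinator's notice, so the table shows where the wording differs and is not a score of protection.

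**Tracing a home reading below 96**

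1. The subject phones as instructed. The reading reaches a physician. The triage sentence does not mention it, but the physician is already dealing with the call.
2. The subject does not phone, but the coordinator or investigator treats the reading as a possible adverse event. Section 8.3.3.2 then requires a clinician to assess its relationship to treatment, and section 8.3.5 requires follow-up.
3. The subject does not phone and the reading is not treated as an adverse event. The coordinator sees it at log review, and 8.1.3 asks for nothing further. This is the gap.

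Route 2 is not certain to catch the reading. Section 8.3.5 describes non-directive questioning, which may not bring out a low reading without symptoms.

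**When the log is next due to be seen.** The log form is returned at Visit 2 (8.1.4), 4 weeks ± 7 days after FMT, which is day 28 − 7 = 21 to day 28 + 7 = 35. The log ends on day 7. The form is therefore next due 21 − 7 = 14 to 35 − 7 = 28 days after the last log day.

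**Exposure.** Each subject has one dose, one 7-day log and one review call. For 15 evaluable women that is 15 × 1 = 15 review calls and 15 × 7 = 105 log days. The documents give no rate of readings below 96 and no rate at which subjects phone in as told. The number of women in route 3 can only be bounded, at 0 to 15.

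**The case against.** The strongest reply is that the main route for a low reading already exists and leads straight to a physician. Section 8.2 tells the subject to phone for that very reason, and nothing stops the doctor from bringing her in; section 8.1.8 allows for contacts outside scheduled visits. On this view the triage sentence is loose drafting and not a decision to ignore low readings. The coordinator also asks about adverse events in the same call. Most of this stands, and it is why the gap is narrow. It does not remove the gap, because the log review is the check for the case in which the subject did not call, and there the written trigger has one side only.

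Two supporting texts also carry less weight than they seem to. The bedside limits in 8.1.2.1 are for recording and create no duty to escalate. The 7-day entry in 8.3.3.3 gives no direction of temperature change and, unlike the entry for later periods, does not refer back to limits already described. The case therefore rests on the lower limit in 8.2 itself.

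A reader might also infer that the call is mistimed, since the Schedule of Activities places it within 7 days of treatment and 8.1.3 at one week. A call on day 7 meets both, so there is no conflict.

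**Conclusion.** The inconsistency is real and minor. Section 8.2 treats a home temperature below 96 as a reason to contact a physician, while notification in 8.1.3 and triage in 8.1.3 and 8.2 are worded for high readings only. The consequence is confined to a low reading that was neither phoned in nor recognised as an adverse event. This assumes that staff follow the text literally; a careful coordinator would probably pass the reading on anyway.

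A reader might infer that low readings have no route to a physician, or that a predictable share of the 15 women would be missed. The documents support neither. The subject's own call is a written route, and any probability would need assumed rates both for low readings and for failure to phone. The textual mismatch is certain; its clinical consequence is not. No endpoint, analysis, sample size or stopping rule changes.

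**What to change.** In 8.1.3, have the coordinator inform the PI of any oral temperature >100.4°F or <96°F. In 8.1.3 and 8.2, replace elevated temperatures in the triage sentences with temperatures outside these limits. All three steps for home readings then use the limits that 8.2 already gives the subject.

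This needs no new visit, test or form, since the log and the call are already planned. The cost is a few extra triage calls, some prompted by measurement error and in any case involving no more than the 15 evaluable women. The same paragraph of 8.1.3 refers to section 9.1.8 for unscheduled visits, which are in 8.1.8; that reference can be corrected in the same amendment.

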8.1.4 Visit 2 (4 weeks post treatment)

Subjects will come to the office for a visit 4 weeks (\pm 7 days) after administration of the FMT treatment or be conducted by telemedicine or telephone.

During their first follow-up visit, the subjects will return to the clinical site in person or via mail:

- Second one-week bowel movement (BM) diary
- Temperature and Adverse Events log form
- Stool specimen

During the visit, the following forms will be completed:

- Medication Log
- Adaption Index
- SF-12
- PFDI-20 (Pelvic Floor Disability Index)
- ABLe Questionnaire
- FIQL (Fecal Incontinence quality of life)
- Bristol Stool Index
- St. Mark's Score
- PGSC (Patient Global Symptom Control)

- Global Impression Improvement
- PACSYM
- PFIQ-7
- AE/SAEs

Subjects will be sent home with a final one-week BM diary that they will return during their 12week visit. The diary will include a card for the collection of all solicited adverse events. Subjects will also be sent home with a stool collection kit to be returned at the 12-week visit or be returned by mail if a telemedicine or telephone visit (optional).

8.1.5 Visit 3 (12 weeks post treatment)

Participants will return to the office for visit 3, twelve weeks (\pm 7 days) after the FMT treatment. The clinical research coordinator will collect final one-week BM diary as well as the stool sample (if available). This visit may occur via telemedicine or telephone, and samples provided via mail or drop off at the clinical site. The following questionnaires will be completed:

- Medication Log
- Adaption Index
- PFIQ-7
- SF-12
- PFDI-20
- ABLe Questionnaire
- FIQL
- Bristol Stool Index
- St. Mark's Score
- PGSC
- Global Impression Improvement
- PACSYM
- AE/SAEs

8.1.6 Phone Contact 2 (End-of-study at 180 days)

The study will conclude after subjects are contacted by telephone or in-person at 180 days (+/-10 days) after final FMT for a final interview focused on potential adverse events.

8.1.7 Early Termination Visits

If the subject decides to withdraw from the study, the subject will be asked to complete all follow-up activities that would have been performed at the next scheduled follow-up visit.

8.1.8 Unscheduled Visits

Data collected from subjects who contact the study team (by telephone or in-person) outside of the scheduled visits (as above) will be associated with the next scheduled study visit, as each study visit is intended to retrospectively cover the time period since the last study visit.

8.2 Safety and Other Assessments

For all women of childbearing potential, a urine pregnancy test will be performed prior to FMT and at all subsequent study visits. If a subject's urine pregnancy test is positive prior to treatment with FMT, the subject will be removed from the study. It is recommended that women not become pregnant as it is unknown how this treatment will effect pregnancies. If a subject does become pregnant on study, the pregnancy will be followed.

To monitor for signs of infection subjects will be required to keep a temperature log for 7 days following FMT (a digital thermometer will be provided). Subjects will be instructed to call the study doctor if their temperature rises above 100.4 degrees or drops below 96 degrees. The study doctor will phone triage patients reporting elevated temperatures and bring them in for a study visit or direct them to the emergency room if necessary.

Subjects will also be provided with a card for the collection of all solicited adverse events in their study diary. The card will be reviewed with the diary for any adverse events.

8.3 Adverse Events and Serious Adverse Events

8.3.1 Definition of Adverse Events (AE)

An adverse event (AE) is any untoward medical occurrence associated with the use of a drug in humans, whether or not considered drug related. Intercurrent illnesses or injuries should be regarded as adverse events.

A pre-existing condition should be recorded as an adverse event if the frequency, intensity, or the character of the condition changes.

8.3.2 Definition of Serious Adverse Events (SAE)

Adverse events are classified as serious or non-serious. A serious adverse event (SAE) is any AE that, in the view of either the Investigator or the Sponsor, is:

- fatal
- life-threatening
- requires or prolongs hospital stay
- results in persistent or significant disability or incapacity
- a congenital anomaly or birth defect
- an important medical event

Important medical events are those that may not be immediately life threatening but are clearly of major clinical significance. They may jeopardize the subject and may require intervention to prevent one of the other serious outcomes noted above. For example, drug overdose or abuse, a seizure that did not result in in-patient hospitalization, or intensive treatment of bronchospasm in an emergency department would typically be considered serious.

All fatal or life-threatening related SAEs or suspected unanticipated serious adverse events (SUSARs) should be reported to the Food and Drug Administration (FDA) within 7 calendar days of knowledge of the event and that non-life threatening SAEs/SUSARs should be reported to the FDA as soon as possible but no later than 15 calendar days after knowledge of the event (21 CFR 312.32).

8.3.3 Classification of an Adverse Event

8.3.3.1 Severity of Event

For adverse events (AEs) not included in the protocol defined grading system, the following guidelines will be used to describe severity.

- Grade 1: Mild Events require minimal or no treatment and do not interfere with the participant's daily activities.
- Grade 2: Moderate Events result in a low level of inconvenience or concern with the therapeutic measures. Moderate events may cause some interference with functioning.
- Grade 3: Severe Events interrupt a participant's usual daily activity and may require systemic drug therapy or other treatment. Severe events are usually potentially life-threatening or incapacitating.
- Grade 4: Life-threatening
- Grade 5: Death

8.3.3.2 Relationship to Study Intervention

All adverse events (AEs) must have their relationship to study intervention assessed by the clinician who examines and evaluates the participant based on temporal relationship and his/her clinical judgment. The degree of certainty about causality will be graded using the categories below. In a clinical trial, the study product must always be considered.

• Definitely Related – There is clear evidence to suggest a causal relationship, and other possible contributing factors can be ruled out. The clinical event, including an abnormal laboratory test result, occurs in a plausible time relationship to study intervention administration and cannot be explained by concurrent disease or other drugs or chemicals.

• Probably Related – There is evidence to suggest a causal relationship, and the influence of other factors is unlikely. The clinical event, including an abnormal laboratory test result, occurs within a reasonable time after administration of the study intervention, is unlikely to be attributed to concurrent disease or other drugs or chemicals, and follows a clinically reasonable response on withdrawal (de-challenge). Re-challenge information is not required to fulfill this definition.

• Potentially Related – There is some evidence to suggest a causal relationship (e.g., the event occurred within a reasonable time after administration of the trial medication). However, other factors may have contributed to the event (e.g., the participant's clinical condition, other concomitant events). Although an AE may rate only as "possibly related" soon after discovery, it can be flagged as requiring more information and later be upgraded to "probably related" or "definitely related", as appropriate.

• Unlikely to be related – A clinical event, including an abnormal laboratory test result, whose temporal relationship to study intervention administration makes a causal relationship improbable (e.g., the event did not occur within a reasonable time after administration of the study intervention) and in which other drugs or chemicals or underlying disease provides plausible explanations (e.g., the participant's clinical condition, other concomitant treatments).

• Not Related – The AE is completely independent of study intervention administration, and/or evidence exists that the event is definitely related to another etiology. Note: there must be an alternative, definitive etiology documented by the clinician.

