5.3 Lifestyle Considerations

After administration of the investigational product (PMT-002) there is no way for investigators to stop or retrieve the product from the subject. Additionally, it is unknown how long the product will remain in the subject's body; thus, subjects should be fully informed that withdraw of the investigational product is not possible and be comfortable with this information prior to administration. Furthermore, as this is a first in human trial for the indication of FI unforeseen side effects are expected.

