6.1.2 Dosing and Administration

A single dose of PMT-002 will be administered via a gastroduodenal tube over 10 to 90 minutes (target 30 minutes). In brief, nasogastric duodenal tube will be placed by a physician and its location will be checked by X-Ray. Once placement is confirmed, the PMT-002 product will be delivered via the NGT using a syringe attached to the end of the tube. Once the product has been delivered, the NGT will be removed. The patient will be observed for 1 hour in the office for potential adverse events.

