8.3.5 Time Period and Frequency for Event Assessment and Follow-Up

Safety will be assessed by monitoring and recording potential adverse effects using the Common Toxicity Criteria version 5.0 (CTCAE V5.0) at each study visit or participant contact (phone call/email). Participants will be monitored by medical histories, physical examinations, and

baseline status. If CTCAE V5.0 grading does not exist for an adverse event, the severity of mild, moderate, severe, life-threatening, and death, corresponding to Grades 1-5, will be used whenever possible.

At each contact with the subject, the investigator will seek information on adverse events by nondirective questioning and, as appropriate, by examination. Adverse events may also be detected when they are volunteered by the subject during the screening process or between visits, or through physical examination, laboratory test, or other assessments. Additionally, the subject study diary will include a card for the collection of all solicited adverse events. Information on all adverse events will be recorded in the source documentation. To the extent possible, adverse events will be recorded as a diagnosis and symptoms used to make the diagnosis recorded within the diagnosis event.

As much as possible, each adverse event or follow-up information will be evaluated to determine:

- 1. Severity grade (CTCAE V5.0 Grade 1-5)
- 2. Duration (start and end dates)

3. Relationship to the study treatment or process – [Reasonable possibility that an AE is related: No (unrelated/ not suspected) or Yes (a suspected adverse reaction)]. If yes (suspected) - is the event possibly, probably, or definitely related to the investigational treatment?

4. Expectedness to study treatment or process – [Unexpected – if the event, severity, and/or frequency is not described in the investigator brochure (if applicable) or protocol].

5. Action taken with respect to study or investigational treatment or process (none, dose adjusted, temporarily interrupted, permanently discontinued, unknown, not applicable).

6. Whether medication or therapy taken (no concomitant medication/non-drug therapy, concomitant medication/non-drug therapy).

7. Whether the event is serious.

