8.3.8 Stopping/Halting Rules

A study wide pause of PMT administration will be instituted if one of the following occur:

- Death attributable to FMT
- Suspected transmission of infection from donor to patient
- If two (2) or more subjects experience the same Grade 3 or higher AE
- If two (2) or more subjects experience an SAE related to the study product
- There is an increase in frequency of long-term adverse events (e.g., IBD, metabolic disease) in > two (2) FMT treatment subjects

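### Probably Related requires a response on withdrawal that a single irretrievable dose cannot give, and the pause rules in 8.3.8 do not say which causality categories count

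*Combined protocol and SAP*

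**What the plan says.** Section 8.3.3.2 grades causality in five steps. Probably Related needs evidence of causation with other influences unlikely, reasonable timing, an event not likely to come from concurrent disease or other drugs, "and follows a clinically reasonable response on withdrawal (de-challenge". It then adds: "Re-challenge information is not required to fulfill this definition". Definitely Related asks that "other possible contributing factors can be ruled out" and does not mention withdrawal. Potentially Related allows that other factors contributed, and the same bullet also calls the category possibly related.

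On the product, Section 6.1.2 states: "A single dose of PMT-002 will be administered via a gastroduodenal tube". Section 5.3 says that after administration "there is no way for investigators to stop or retrieve the product from the subject", and that participants must understand that "withdraw of the investigational product is not possible".

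Relatedness is used in two further places that matter here. Section 8.3.5, item 3, first asks whether there is a reasonable possibility that the event is related, where yes means a suspected adverse reaction. If yes, it asks: "is the event possibly, probably, or definitely related to the investigational treatment". Section 8.3.8 lists the triggers for a study-wide pause. One reads "If two (2) or more subjects experience an SAE related to the study product"; another is a death attributable to FMT. Neither refers to the scale in 8.3.3.2 or to 8.3.5.

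**The concern.** The scale borrows a criterion from drugs that can be stopped. Here there is nothing to withdraw once the dose is in. An assessor who follows the text cannot award the middle grade to an event that appears after dosing, however likely the product is as the cause. This bites hardest on the late events that Section 8.3.3.3 asks staff to watch for, transmitted infection and metabolic change, because these may persist and show no response of any kind. The scale is also out of order: the weaker grade, Probably, carries a requirement that the stronger grade, Definitely, does not. The route in 8.3.3.2 for upgrading an event from possibly to probably related is blocked in the same way.

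Safety is a primary objective, and Section 4.1 says the study is to supply safety data for a later randomised trial. Causality grades that cannot be applied as written will be applied inconsistently. The practical stake is the pause rule: if two women have different SAEs that are both likely product effects but graded Potentially Related, 8.3.8 does not say whether dosing pauses.

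**Working it through.** The plan gives no figure on this point, so the main check sets the sections side by side.

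1. *Is de-challenge required?* In 8.3.3.2 it is joined to the other elements by a plain conjunction. The next sentence waives re-challenge and says nothing of de-challenge. On its face it is required.
2. *Can it be met?* Section 6.1.2 gives one dose, and Section 5.3 says it cannot be stopped, retrieved or withdrawn after administration. For events after dosing, it cannot literally be met. The exception is an event during the infusion, since Section 6.2.1 foresees that administration may be stopped.
3. *Where does a likely effect go?* If other causes are ruled out, up to Definitely Related. Otherwise, down to Potentially Related.
4. *Does the downgrade remove it from reporting?* Section 8.3.5 keeps possibly related events under suspected adverse reactions. Section 8.3.6 sends every SAE to the Sponsor whatever its cause. Section 8.3.7 ties the 7-day FDA report to suspected reactions and describes the 15-day report as a SUSAR, in which the first S stands for suspected. So it should not.
5. *Does it remove it from a pause trigger?* Section 8.3.8 does not say. Under the 8.3.5 definition, no; if related is taken to mean probably or definitely, yes.

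For the scale of step 5 only, let p be the true risk per woman of a product-related SAE and f the share of those events not counted as related. Both are assumptions; the documents give neither. With the 15 evaluable women of Section 9.3 and q = p(1 − f):

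P(2 or more women counted) = 1 − (1 − q)^15 − 15q(1 − q)^14

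For p = 10% and f = 0, q = 0.10: 1 − 0.2059 − 0.3432 = 0.451. For p = 10% and f = 0.5, q = 0.05: 1 − 0.4633 − 0.3658 = 0.171.

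| p | f = 0 | f = 0.25 | f = 0.5 | f = 0.75 | f = 1 |
|---|---|---|---|---|---|
| 5% | 17.1% | 10.7% | 5.3% | 1.5% | 0% |
| 10% | 45.1% | 31.2% | 17.1% | 5.3% | 0% |
| 15% | 68.1% | 51.6% | 31.2% | 10.7% | 0% |
| 20% | 83.3% | 68.1% | 45.1% | 17.1% | 0% |

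The column f = 0 is what follows if 8.3.8 is read with 8.3.5. The other columns apply only under the narrow reading. They concern this one trigger and ignore the other pause rules.

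**The case against.** The strongest reply is that the protocol already supplies the mapping. Section 8.3.5 is the only place that turns the grades into a yes or no, and it puts possibly, probably and definitely related together under yes. Section 8.3.3.2 itself uses possibly related for its Potentially Related category, so the two labels can be matched. This stands for reporting. A reader might infer that likely product effects would escape expedited reporting under 8.3.7; steps 4 and 5 separate the two questions, and the documents do not support that inference. Nor do they support the inference that the safety results would be distorted: the primary safety endpoint in Section 3 counts adverse events, SAEs and events of special interest without splitting them by cause, and Section 9.4.1 plans descriptive summaries.

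It can also be said that the category is not wholly empty. An event during infusion could be judged on stopping, and 8.3.3.2 leaves room for clinical judgement, so an assessor might treat resolution over time as the response. That stands in part, but it does not help with delayed or persistent events, and it asks assessors to read the text as something other than what it says.

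Finally, other triggers in 8.3.8 do not rest on the causality grade. The same Grade 3 or higher event in two women pauses dosing whatever its cause, and one suspected donor transmission is enough. A DSMB also reviews safety. These are real but partial backstops: two different SAEs, neither a suspected transmission nor a death, could fall between them.

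**Conclusion.** The definition of Probably Related is wrong as written for this product. For events after dosing it sets a condition that Sections 5.3 and 6.1.2 say cannot arise, and it leaves the scale inverted. That conclusion rests on the text alone.

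The safety exposure that follows is narrow. It needs two different SAEs, both graded Potentially Related, and staff who read related in 8.3.8 more strictly than 8.3.5 does. In that case the loss on this trigger could be large (at p = 10%, from 45.1% to 17.1% if half the events are not counted), but p and f are assumptions, and under the 8.3.5 definition the loss is zero. The documents give no basis for estimating what share of events would be affected. The term attributable, used for deaths, has the same gap, since it is not a grade on the scale. This is worth correcting because the correction is cheap, not because under-reporting has been shown.

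**What to change.** - In 8.3.3.2, remove the de-challenge and re-challenge wording from Probably Related, so that the category fits a single dose that cannot be retrieved.
- Use one label, either potentially or possibly related, in both 8.3.3.2 and 8.3.5.
- Have the sponsor reconcile related and attributable in 8.3.8 with the 8.3.5 definition of a suspected adverse reaction, and state which causality categories qualify for each trigger. Which categories should count toward a pause is for the sponsor to decide; the point is that the text should say.

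The cost is a wording change to the protocol and to the labels on the adverse event form. Some events will be graded probably rather than potentially related. The number of subjects needed for each pause trigger stays as it is.
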